10.9. Study Completion

All enrolled subjects will be followed for the duration of 12 months post procedure. A subject's participation in the study will be considered complete after the 12-month follow-up visit. Subjects who are enrolled but not implanted with a WATCHMAN FLX Pro Device in the correct position during the implant procedure will be followed for safety through 12 months after the initial attempted implant procedure by telephone or review of clinical files

but will not undergo imaging assessments or evaluation of biochemical markers including measures of coagulation, platelet and endothelial activation and inflammation.

10.10. *Source Documents*

It is preferable that original source documents, when available, are maintained at the investigative center. In lieu of original source documents, certified copies are required to be maintained. A certified copy is a copy (irrespective of the type of media used) of the original record that has been verified (i.e., by a dated signature or by generation through a validated process) to have the same information, including data that describe the context, content, and structure, as the original. Source documentation includes but is not limited to those items noted in **Table 10.10-1**. Source documentation provided to the Sponsor for assessment/adjudication will be deidentified per local law and regulations.

Table 10.10-1: Source Documentation Requirements

Requirement	Disposition
Printed, optical, or electronic document containing source data. Examples may include but are not limited to the following: hospital records; laboratory notes; device accountability records; photographic negatives; radiographs; records kept at the investigation center, at the laboratories and at the medico-technical departments involved in the clinical investigation.	Retain at center

Note 1: Please see **Table 25.2-1** for definitions of “source data” and “source document.”

10.11. *Local Laboratory/Vendor Documentation*

Appropriate certifications and documentation records are required to be maintained at the investigative center for local laboratory/vendor work.

11. Statistical Considerations

11.1. *Endpoints*

11.1.1. *Primary Endpoint*

The primary endpoint, which is not a powered endpoint, is device surface morphology (inclusive of tissue coverage) post implant procedure as assessed over 14 days, 45 days, and 3 months post implant procedure using the serial advanced imaging modalities of cardiac computed tomography (CT) and transesophageal echocardiography (TEE). Descriptive statistics will be used to report outcomes for this non-powered primary endpoint. For this single-arm feasibility study with no formal pre-specified hypothesis, sample size estimates are not applicable. To support the stated objectives of this study, the study sample size has been limited to a maximum of 50 enrolled subjects.

11.1.2. Additional Procedural and Post-procedure Measurements

Procedural and post-procedure information will be collected as detailed in the clinical study schedule (**Table 10.1-1**) and will be summarized using descriptive statistics for continuous variables (e.g., mean, standard deviation, n, minimum, maximum) and frequency tables or proportions for discrete variables. The Kaplan-Meier product-limit method will be used to estimate rates for time-to-event endpoints. Adverse event and SAE rates will be reported.

11.2. General Statistical Methods

All statistical analyses will be performed using the SAS System software, version 9.2 or later (Copyright[©] 2000 SAS Institute Inc., [name], USA. All rights reserved).

All statistical analyses will be conducted according to applicable Standard Operating Procedures, Work Instructions, and the study-specific statistical analysis plan.

Statistical models that account for censored data will be employed in appropriate circumstances (e.g., for time-to-event outcomes).

11.2.1. Analysis Sets

Outcomes in WATCHMAN FLX Pro CT will be assessed on an ITT basis and an implanted basis. The ITT analysis set includes all subjects who sign an ICF (see Section 19) approved by the IEC and who are enrolled in the study (see Section 9.1 for point of enrollment), whether or not the WATCHMAN FLX Pro device is implanted. The implanted analysis set includes ITT subjects who are successfully implanted with the study device in the correct position.

11.2.2. Control of Systematic Error/Bias

All subjects who have signed the ICF, met the inclusion/exclusion criteria (Section 8.2 and Section 8.3) and are selected to receive a study device will be eligible for enrollment in the study (see Section 9.1 for point of enrollment). The selection of subjects will be made from the Investigator's usual case load. The study center's heart team assessments and imaging measurements before device placement will contribute to the determination of subject eligibility for the study.

To control for inter-observer variability, data from an independent core laboratory (see Section 12) will be used for analysis at pre-specified time points. An independent CEC (see Section 20.1.1) will adjudicate study endpoint related clinical events (see Section 6.2).

11.2.3. Number of Subjects per Investigative Center

A single center may enroll up to 50 subjects.

11.2.4. Reporting Events

For all subjects who receive a study device, all events that occur from the time of enrollment (see Section 9.1) will be reported. Subjects who are enrolled and have an attempted procedure but do not receive a study device will be followed for safety through 12 months after the initial attempted implant procedure by telephone or review of clinical files but will not undergo imaging assessments or evaluation of biochemical markers including measures of coagulation, platelet and endothelial activation and inflammation. For these subjects, events from the time of enrollment to 12 months post procedure will be reported.

For time-based clinical events, the cut-off for events for 14-day endpoints will be 14 days, for 45-day endpoints it will be 45 days, for 3-month endpoints it will be 90 days, and for 1-year endpoints it will be 365 days. For events at discharge or 7 days post-procedure, the cut-off for events will be the earlier of the date of discharge or 7 days post-procedure for each subject.

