The iterative WATCHMAN FLX™ LAAC Device (WATCHMAN FLX) was assessed in the prospective, nonrandomized, multicenter PINNACLE FLX study (N=400)²⁶. The primary safety end point was the occurrence by hospital discharge or 7 days post procedure, whichever came later, of one of the following events: death, ischemic stroke, systemic embolism, device- or procedure-related events requiring cardiac surgery. The primary effectiveness end point was the incidence of effective LAA closure (peri-device flow ≤5 mm), as assessed by the echocardiography core laboratory at 12-month follow-up. The primary safety endpoint was met with a rate of 0.5% and a 1-sided 95% upper confidence interval (CI) of 1.6%, which was significantly below the performance goal of 4.2% ($P<0.0001$). The primary effectiveness endpoint was met with a rate of 100% and a 1-sided 95% lower CI of 99.1%, which met the performance goal of 97.0% ($P<0.0001$). WATCHMAN FLX received CE mark in 2015 and FDA approval in 2020²⁷.

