Commercially available access systems to use with WATCHMAN FLX Pro include the WATCHMAN® Access System and the WATCHMAN™ TruSeal™ Access System. They all have a dilator and access sheath, which are used to gain access to the LAA once initial transseptal entrance into the left atrium has been established. The distal end of the access sheath is available in multiple curve styles for coaxial placement in the LAA. The distal tip contains a marker band for in situ visualization.

Once the access sheath is positioned in the left atrium and the dilator has been removed, the sheath serves as a conduit for the WATCHMAN FLX Pro Delivery System. The delivery system is introduced into the access sheath and the components snap together to act as one during device implantation. Additional product information can be found in the associated Access System IFUs.

The commercially available access systems are required to be used in the study but are not themselves subject of the clinical investigation. They are commercially-labeled and will be managed per each institution's standard practice.

6. Study Objectives and Endpoints

6.1. *Study Objectives*

The primary objective of this study is to measure device tissue coverage post-implantation of WATCHMAN FLX™ Pro using the serial advanced imaging modalities of cardiac CT and TEE and assess its relationship, if any, to clinical events.

Table 6.1-1 provides an overview of the study objectives and endpoints and a rationale for the specific endpoints. Additional information on endpoints is provided in Section **6.2**.

Table 6.1-1: Overview of Objectives and Endpoints

Objective	Endpoint	Rationale for Endpoint
Primary Endpoint	Device surface morphology (inclusive of tissue coverage) post implant procedure as assessed over time using the serial advanced imaging modalities of cardiac computed tomography and transesophageal echocardiography	Imaging surveillance at follow-up allows assessment of device tissue coverage, peri-device leaks, and device-related thrombus, which may be associated with late thromboembolic events. Data are evaluated by an independent core laboratory.
Additional Measurements of Safety and Effectiveness		
Evaluate safety of the implant and the procedure	Safety measures at discharge, 14 days, 45 days, 3 months, and 12 months post implant procedure	Safety assessments, including early cardiac safety, with events adjudicated by an independent Clinical Events Committee

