6.2.2. Additional Measurements

Additional endpoint measurements will be collected peri- and post-procedure, predischarge, and at 14 days, 45 days, 3 months, and 12 months after the implant procedure, unless specified otherwise below.

- Safety endpoints (adjudicated by an Independent Clinical Events Committee [CEC]):
 - All-cause mortality (cardiovascular/unknown and non-cardiovascular)
 - Stroke (disabling and non-disabling; ischemic and hemorrhagic)
Note 1: For subjects diagnosed with a neurological event (e.g., stroke, transient ischemic attack [TIA]), mRS and NIHSS should be performed after the event. It is recommended that the subject be contacted regarding mRS assessment at 90 ± 14 days following any suspected stroke; the simplified mRS questionnaire³⁸ may be used for this follow-up assessment. It is recommended that imaging be performed after the event to screen for device related thrombus (DRT). If performed, imaging results should be sent to the core laboratory.
 - Systemic embolism
 - Bleeding: International Society on Thrombosis and Haemostasis (ISTH) major and non-major clinically significant^{39,40}
 - Procedural bleeding (≤ 7 days post-procedure)
 - Non-procedural bleeding (> 7 days post-procedure)
 - Pericardial effusion/tamponade requiring pericardiocentesis or surgery
- Device Success: defined as implantation of a WATCHMAN FLX Pro device without in-hospital mortality.
- Assessments by serial imaging modalities (CT and TEE, optional cardiac magnetic resonance imaging [MRI]) at 14 days, 45 days, and 3 months (TEE optional at 3 months if there is no leak at 45 days). Data will be evaluated by an independent core lab.
 - Device seal at 45 days post implant procedure (see **Note 2** and **Note 3**)
 - Device-related thrombus (including hypoattenuated thickening [HAT] per CT analysis)
- **Note 2:** Results are classified as no leak, leak > 0 and ≤ 5 mm, or leak > 5 mm
Note 3: TEE should be performed at 12 months if the 3-month TEE assessment suggests a leak > 5 mm or the 3-month CT assessment suggests a leak > 3 mm; results must be sent to the core laboratory.

- 4D MRI flow analysis (if available) of the left atrium (LA) and LAA before (14 days prior to the implant procedure) and serially after device implant (at 14 days, 45 days, and 3 months); data will be evaluated by an independent core lab.

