9.1. Point of Enrollment

A subject is considered enrolled in the study when the subject or the subject's legally authorized representative signs an ICF approved by the IEC. No study-specific tests, procedures, etc. can take place until the ICF is signed. A subject who is determined to not

meet study specific clinical eligibility criteria after signing consent will be considered a screen failure (see **Table 9.4-1**) and will not count towards the enrollment ceiling.

9.2. *Withdrawal*

All subjects enrolled in the clinical study (including those withdrawn from the clinical study) shall be accounted for and documented. If a subject withdraws from the clinical investigation the reason(s) shall be reported. Reasons for withdrawal include but are not limited to physician discretion, subject choice to withdraw consent, or death. Reasons for study exit will be captured in the secure electronic data capture (EDC) system. If such withdrawal is due to problems related to device safety or performance, the investigator shall ask for the subject's permission to follow his/her status/condition outside of the clinical study.

While all efforts will be made to minimize attrition, subjects may withdraw from the study at any time, with or without reason, and without prejudice to further treatment. Withdrawn subjects will not undergo any additional study follow-up, nor will they be replaced. The investigator may discontinue a subject from participation in the study if the investigator feels that the subject can no longer fully comply with the requirements of the study or if any of the study procedures are deemed potentially harmful to the subject. Data that have already been collected on withdrawn subjects will be retained and may be used for analysis unless local regulations apply. No new data will be collected after subject withdrawal.

All applicable case report forms up to the point of subject withdrawal and an "End of Study" form for the subject must be completed. If the withdrawal is due to investigator discretion, the investigator should follow-up with the subject per standard of care.

9.3. *Lost to Follow-Up*

All enrolled subjects will be followed for up to 12 months post-procedure.

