20.1.1. Clinical Events Committee

A Clinical Events Committee (CEC) will be used in this study. The CEC is an independent group of individuals with pertinent expertise, including cardiovascular interventional therapy, cardiovascular surgery, and neurology, which reviews and adjudicates important endpoints and relevant adverse events reported by study investigators. The CEC will review a safety event dossier, which may include copies of subject source documents provided by study centers and adjudicate study endpoint related clinical events. The responsibilities, qualifications, membership, and committee procedures of the CEC are outlined in the CEC Charter.

The CEC will review the following events for this study.

- All-cause mortality (cardiovascular/unknown and non-cardiovascular)
- Stroke (disabling and non-disabling; ischemic and hemorrhagic)
- Systemic embolism
- Bleeding: ISTH major and non-major clinically significant bleeding including procedural (≤ 7 days post-procedure) and non-procedural (>7 days post-procedure)
- Pericardial effusion/tamponade requiring pericardiocentesis or surgery
- Other events, at the discretion of BSC

21. Suspension or Termination

21.1. *Premature Termination of the Study*

Boston Scientific Corporation reserves the right to terminate the study at any stage but intends to exercise this right only for valid scientific or business reasons and reasons related to protection of subjects. Investigators, associated IECs, and regulatory authorities, as applicable, will be notified in writing in the event of study termination.

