Outcomes in WATCHMAN FLX Pro CT will be assessed on an intention-to-treat (ITT) basis and an implanted basis. The ITT analysis set includes all subjects who sign an Informed Consent Form approved by the Independent Ethics Committee (IEC) and are enrolled in the study, whether or not the WATCHMAN FLX Pro device is implanted. The implanted analysis set includes ITT subjects who are successfully implanted with the study device in the correct position.

Endpoints are listed below. Measurements will be collected peri- and post-procedure, predischarge, and at 14 days, 45 days, 3 months and 12 months after the implant procedure, unless specified otherwise.

The primary endpoint is device surface morphology (inclusive of tissue coverage) post implant procedure as assessed over time using the serial advanced imaging modalities of cardiac computed tomography (CT) and transesophageal echocardiography (TEE).

Additional endpoints will include the following:

- Endpoints adjudicated by an Independent Clinical Events Committee (CEC):
 - All-cause mortality (cardiovascular/unknown and non-cardiovascular)
 - Stroke (disabling and non-disabling; ischemic and hemorrhagic)
 - **Note 1:** For subjects diagnosed with a neurological event (e.g., stroke, transient ischemic attack [TIA]), mRS and NIHSS should be performed after the event. It is recommended that the subject be contacted regarding mRS assessment at 90±14

days following any suspected stroke; the simplified mRS questionnaire may be used for this follow-up assessment. It is recommended that imaging be performed after the event to screen for device related thrombus (DRT). If performed, imaging results should be sent to the core laboratory.

- Systemic embolism
- Bleeding: International Society on Thrombosis and Haemostasis (ISTH) major and non-major clinically significant
 - Procedural bleeding (≤ 7 days post-procedure)
 - Non-procedural bleeding (> 7 days post-procedure)
- Pericardial effusion/tamponade requiring pericardiocentesis or surgery
- Endpoints not adjudicated by an Independent Clinical Events Committee (CEC):
- Device success: defined as implantation of a WATCHMAN FLX Pro device without in-hospital mortality
- Assessments by serial imaging modalities (CT and TEE, optional cardiac magnetic resonance imaging [MRI]) at 14 days, 45 days, and 3 months (TEE optional at 3 months if there is no leak at 45 days). Data will be evaluated by an independent core lab.

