9.3. Rules and Definitions

Binary event rates (proportions) will be calculated on a per subject basis.

The number of subjects included in the outcome rates will be based on subjects who have adequate follow-up (see Section 9.4) and/or have experienced any events.

For baseline categorical variables, “unknown” responses and missing values will not be counted in rate denominators.

The date of last follow-up will be the latest of the following dates for each subject: date of a major event with CEC adjudication, index procedure date, discharge date, and scheduled follow-up visit date.

Days to (event or last known status) = (event or status) date minus procedure date.

Length of hospital stay = discharge date minus procedure date.

In-hospital event rates are calculated as the proportion of subjects who experience the specified event from index procedure through day of discharge out of all subjects enrolled.

Out-of-hospital event rates are calculated as the proportion of subjects who experience the specified event from the day after discharge through the number of days as specified out of all subjects who were discharged following index procedure and have adequate follow-up or have experienced the event as specified.

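### Protocol 11.2.4 stops early events at the earlier of discharge or day 7, which would cut short procedural bleeding or in-hospital safety if applied to them (minor)

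*Protocol*

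**What the plan says.** Protocol 11.2.4 (Reporting Events) sets cut-offs of 14, 45, 90 and 365 days for the scheduled time points. Its last sentence deals with events at discharge or 7 days and states that "the cut-off for events will be the earlier of the date of discharge or 7 days post-procedure for each subject".

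The early safety measures are defined elsewhere, each with its own window:

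- **Bleeding.** Protocol 6.2.2 has "Procedural bleeding (≤ 7 days post-procedure"; the events committee list in Protocol 20.1.1 has "procedural (≤ 7 days post-procedure) and non-procedural (>7 days post-procedure"; SAP 5.2 has "Non-procedural bleeding (> 7 days post-procedure" as the complementary class. None of these refers to discharge.
- **Safety at discharge.** Protocol Table 6.1-1 lists "Safety measures at discharge, 14 days, 45 days, 3 months, and 12 months post implant procedure", with no day-7 limit. Device success (Protocol 6.2.2) depends on the absence of in-hospital death, again with no limit in days.
- **In-hospital rates.** SAP 9.3 counts events "from index procedure through day of discharge out of all subjects enrolled".

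The SAP does not contain the earlier-of sentence. Its 9.4 table has rows for 14 days, 45 days, 3 months and 1 year, and none for discharge or day 7. A footnote to that table describes the one-year maximum of 365 days as the end of the visit window.

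**The concern.** The 11.2.4 sentence is an operative counting rule, but no endpoint in Protocol 6.2 or SAP 5.2 is called a discharge-or-7-days endpoint. Someone programming an early safety table has to decide where it applies, and the only candidates are procedural bleeding and the discharge or in-hospital measures. On each of these the rule conflicts with the measure's own definition whenever discharge does not fall on day 7.

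Bleeding has the more awkward consequence. The two classes are meant to divide all bleeds at day 7. If the procedural class is closed at an earlier discharge, bleeds between discharge and day 7 belong to neither class. For long stays the in-hospital count would stop at day 7 while the subject is still an inpatient. In both directions the early count can only fall.

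**Working it through.** **Inputs.** Count the procedure day as day 0 (SAP 9.3 takes event date minus procedure date) and let D be the day of discharge.

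- Cut-off under Protocol 11.2.4: min(D, 7).
- Procedural bleeding window (Protocol 6.2.2, 20.1.1; SAP 5.2): days 0 to 7.
- In-hospital window (SAP 9.3): days 0 to D.

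The documents give no length of stay, so D is an assumed range.

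**Days lost.** Procedural bleeding loses 7 − min(D, 7) days. The in-hospital window loses D − min(D, 7) days.

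| D | 11.2.4 cut-off | Lost from procedural bleeding | Lost from in-hospital window |
|---|---|---|---|
| 0 | 0 | 7 | 0 |
| 1 | 1 | 6 | 0 |
| 2 | 2 | 5 | 0 |
| 3 | 3 | 4 | 0 |
| 5 | 5 | 2 | 0 |
| 7 | 7 | 0 | 0 |
| 8 | 7 | 0 | 1 |
| 10 | 7 | 0 | 3 |
| 14 | 7 | 0 | 7 |

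For any D other than 7, exactly one of the two windows is shortened. These are days of observation, not shares of events; the documents give no timing of bleeds from which to convert them.

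**The unclassified bleed.** Take discharge on day 1 and a bleed on day 4. Since 4 > min(1, 7) = 1, the bleed is outside the procedural count under 11.2.4. Since 4 ≤ 7, it is not non-procedural either. It does enter a 14-day count of all bleeds, because 4 ≤ 14.

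**Size.** With 50 subjects (the protocol maximum) in the denominator, one omitted event is 1/50 = 2.0 percentage points.

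**If each measure keeps its own window.** Bleeding through day 7 and in-hospital measures through day D lose 0 days for every D.

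**SAP 9.4 footnote.** The window starts reproduce from the visit schedule in Protocol Table 10.1-1: 14 − 3 = 11, 45 − 15 = 30, 90 − 30 = 60, 365 − 30 = 335. The end of the one-year window is 365 + 30 = 395, so 365 is the target day there, as the maximum is in the other rows. Protocol 11.2.4 also uses 365 as the one-year cut-off. Only the label is wrong.

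**The case against.** The strongest reply is that nothing in the SAP changes. Protocol 11.2 says that analyses follow the study-specific SAP. The SAP omits the earlier-of rule, states bleeding as through day 7 or after day 7, and runs in-hospital rates to discharge. SAP 9.4 also says that its method extends to other time points with the day numbers changed, so a 7-day cut-off already follows from it. Harm requires someone to let one unattached protocol sentence override definitions that are repeated in several places. This stands, and it is why the point is minor and conditional. It does not make the sentence correct: either it governs something and conflicts with that measure's definition, or it governs nothing and should go.

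A charitable reading is that the sentence covers two separate time points, discharge and day 7. But it then assigns each subject a single date, the smaller of the two, so it cannot preserve both.

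A reader might also set the sentence beside the predecessor-device study in Protocol 4.1.2, whose primary safety endpoint covered "the occurrence by hospital discharge or 7 days post procedure, whichever came later". It is tempting to infer that 11.2.4 is a miscopied version, or that early rates here would look better than that study's. The documents support neither inference. They do not say that the rule was carried over, that endpoint is a different composite, and no comparison with its rate is planned.

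**Conclusion.** The point holds as a minor inconsistency in the protocol. Read literally, the last sentence of 11.2.4 contradicts the bleeding definition for discharge before day 7 and the in-hospital window for stays beyond day 7. It can also leave a bleed in neither class.

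The size is small: 2.0 percentage points per omitted event, assuming all 50 subjects are enrolled and in the denominator. How many events would be affected cannot be estimated without length of stay and event timing. The primary imaging endpoint is untouched, no hypothesis is tested, and the omitted events still count at 14 days or later.

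A reader might infer that the planned early safety tables will be wrong. The documents do not show that, because the SAP keeps the proper windows. Nor does the SAP 9.4 footnote alter any one-year rate, since the cut-off of 365 agrees with the protocol.

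**What to change.** Delete the last sentence of Protocol 11.2.4, or replace it with:

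*Procedural bleeding is counted from the procedure through day 7, whether or not the subject has been discharged; later bleeding is non-procedural. In-hospital death, device success and safety measures at discharge are counted through the day of discharge, whatever day that is.*

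Put the same windows in SAP 9.3. A blanket later-of rule is not needed, because no endpoint in this study uses a combined window. It would also run past day 7 for long stays and past discharge for short ones.

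In the same SAP amendment, correct the 9.4 footnote: 365 is the target day, the visit window is days 335 to 395, and the cut-off stays at 365.

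No new data are needed. Protocol 11.3 allows the SAP change in an amended plan approved before the analyses. The SAP supplied still refers to protocol Rev C and 25 subjects, so it needs revision in any case. Changing the protocol sentence needs ethics committee approval (Protocol 15.3) and can wait for the next amendment. Early counts may come out slightly higher than under the literal rule.
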